3.2 Exclusion Criteria

[figure not shown]
All individuals meeting any of the exclusion criteria at baseline will be excluded from study participation:

- 3.2.1** Main trial: Age younger than 50 years or older than 75 years; Sub-study: Age younger than 45 years or older than 49 years
- 3.2.2** Not at average risk for CRC (“average risk” is defined as those patients who do not have any of the following: history of CRC, colonic adenomas, family history of CRC, or diagnosis of inflammatory bowel disease)
- 3.2.3** Record of FOBT/FIT within the past 12 months or colonoscopy within 10 years, sigmoidoscopy within 5 years; barium enema within 5 years, or CT colonography within 10 years of the EHR query date
- 3.2.4** Record of any CRC diagnosis or total colectomy
- 3.2.5** Not an active patient (not seen within the past 18 months) of RCCHC or BRH

Patients will not be invited to participate in an interview if they meet additional exclusion criteria: be assigned to study Arm 1, do not return a FIT as a participant in the screening program, or have a negative (normal) FIT result as a participant in the screening program.

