In addition, we will work with RCCHC to promote uptake of CRC screening among their screening-eligible patients aged 45-49. We will enroll all patients who are aged 45-49 and meet study eligibility criteria. Based on a recent query of RCCHC’s EHR, there are approximately 450 patients aged 45-49 who currently are eligible for CRC screening. We will compare screening completion before and after mailed FIT outreach and will assess the impact of envelope appearance on FIT return.

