3.0 PATIENT ELIGIBILITY

We will use the inclusion and exclusion criteria below to guide our electronic health record (EHR) query to identify eligible patients for the main trial and added cohort of patients ages 45-49.

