4.3 Study Details

4.3.1 Cohort Ascertainment

Our study team will work with RCCHC and BRH to identify the population of patients at each site who meet study inclusion criteria (see section 3.1), using an automated query of the EHR at each site. Per protocols from two similar projects, all patients meeting inclusion criteria will be initially included in the study cohort. Because EHR records are based on best available information and may not reflect screenings performed at another facility, our study materials will include a phone number for patients to contact the study team to self-identify as ineligible. We will select patients for inclusion randomly from the cohort and replace as needed to reach the goal of up to 4,000 Main Trial participants from RCCHC and BRH and an additional 450 sub-study participants from RCCHC. Each FQHC will query their own EHR to identify patients who meet eligibility criteria. Designated staff at each FQHC will securely transfer the queried patient information from their EHR to a folder accessible only to IRB-approved study team members on a secure UNC server (UNC Teams folder designated specifically for each FQHC). The data set will contain, but not necessarily be limited to, patient name, age, sex, race/ethnicity, email address, mailing address, primary care provider, and the date of the most recent visit with one of the FQHC's primary care providers. Only authorized clinic and UNC project team representatives will be able to upload or remove data to UNC Teams. Each FQHC site will have its own folder, which will prevent access to data of patients not seen at their clinic. A member of the UNC project team will then transfer the patient data from UNC Teams to a REDCap database accessible only to UNC project team members.

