7.2 Sample Size and Accrual

Main Trial

Our project funding supports a sample size of up to 4,000 patients at two clinical sites who are eligible for CRC screening. Using a 1:1 randomization approach, up to 2,000 RCCHC patients and up to 2,000 BRH patients will be randomized to the two study arms. For each FQHC, up to 1,000 patients will be randomized to each of the two arms. Our statistician performed formal power calculations for our primary study outcome comparing CRC screening completion for the intervention arm vs. the control arm, stratified by patient insurance status (4 strata: Medicare, Medicaid, commercial/private, and self-pay/other). Based on previous research, we anticipate that 25% of those receiving the intervention will complete CRC screening, and 17% of patients in the usual care arm will complete screening (8% difference between arms). We need 492 participants per arm, per strata to have at least 80% power to detect an 8% difference between study arms at 1-sided alpha level 0.0125 (3,936 participants total, which can be rounded up to 4,000). We calculated power by SAS PROC Power (SAS Institute, Cary, NC).

Sub-study (ages 45-49)

Sample size in this additional substudy is determined by feasibility and resource constraints. We have the resources to do intervention testing in this new age group (45-49) in a single clinic site. We will identify the cohort of participants who are eligible for screening on a given index date. We estimate 500 patients are in this age group and eligible for screening. We estimate that approximately 10%, i.e., 50 individual patients, will be current with screening at baseline. We will conduct the mailed intervention on the approximately 450 patients who are not current and then assess the screening rate at 60 days in same cohort. For outcome 2, we will use a 1:1 randomization approach to randomize patients the patients who are not current with screening to the two experimental study arms (envelope type).

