Our statistician performed formal power calculations for our study outcomes of change in CRC screening rate (pre-post) for this age group, as well as FIT return compared across the two arms. **Outcome 1:** We will observe baseline and post-intervention status of CRC for subjects who are not screened at baseline. For those who screened at baseline, we will not observe post-intervention CRC status, but we assume a high post-intervention screen rate for such subjects if they receive intervention before they receive screening. This leads to a paired binary data problem, and we test if the conversion rate (from not screened to screened) is high enough. A sample size of 500 achieves 80% power to detect an odds ratio of 2.922 using a two-sided McNemar test with a significance level of 0.05. This calculation is based on a difference between two paired proportions of 0.034 (P10-P01), where P10 (about 0.052) refers to the proportion of subjects who not screen at baseline but screen after intervention and the proportion (P01) of screen at baseline but not screen after intervention. This is an assumed number because we are not able to observe it but assume it's a very small number) is 0.018. The proportion of discordant pairs is 0.07. We will report baseline screening rate and post-intervention screening rate. **Outcome 2:** With 225 patients per arm, we reach 80% power, with 1-sided alpha 0.05, to detect a difference between the group FIT mail back rates of 0.102. The FIT mail back rate in Group 1 (the treatment group) is assumed to be 0.20 under the null hypothesis and 0.302 under the alternative hypothesis. The rate in Group 2 (the control group) is 0.20. We calculated power using SAS PROC Power (SAS Institute, Cary, NC).

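### The entry criteria and the sample-size section define different cohorts for sub-study Outcome 1: about 450 patients with essentially none current at baseline, or 500 with about 50 current whose later status will not be observed.

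*Combined protocol and SAP*

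**What the plan says.** Section 3.0 states that the criteria are used "to guide our electronic health record (EHR) query to identify eligible patients for the main trial and added cohort of patients ages 45-49". Criterion 3.2.3 excludes patients with a "Record of FOBT/FIT within the past 12 months or colonoscopy within 10 years, sigmoidoscopy within 5 years", and goes on to list barium enema and CT colonography. Section 3.2 opens with "All individuals meeting any of the exclusion criteria at baseline will be excluded from study participation". Only the age limits differ between the main trial and the sub-study.

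Section 1.2 says that "there are approximately 450 patients aged 45-49 who currently are eligible for CRC screening" and that all who meet the criteria will be enrolled. Section 4.3.1 has each clinic query its own EHR for patients meeting the criteria and sets a target of "an additional 450 sub-study participants from RCCHC".

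Section 7.2 starts from 500 patients aged 45-49, whom it also calls eligible for screening. It adds: "We estimate that approximately 10%, i.e., 50 individual patients, will be current with screening at baseline". The 450 who are not current are mailed, and the screening rate is assessed at 60 days in the same cohort. Under Outcome 1, the power statement uses 500 pairs and a two-sided McNemar test. It says that the post-intervention status of patients screened at baseline will not be observed, so P01 is an assumed value. It ends: "We will report baseline screening rate and post-intervention screening rate".

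**The concern.** The same label, eligible for screening, is attached to 450 patients in 1.2 and to 500 in 7.2, and the second group includes 50 whom 3.2.3 removes. Take a 47-year-old with a colonoscopy three years ago. Section 7.2 counts this patient in both the numerator and the denominator of the baseline rate, whereas 3.2.3 excludes the same patient. A programmer who follows 4.3.1 would not retrieve the record.

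The two cohorts also answer different questions. In the 7.2 cohort, Outcome 1 is the change in the clinic's screening rate for this age group. In the Section 3 cohort, it is the proportion of patients selected as unscreened who then get screened. A McNemar test adds little there, because selection leaves discordance possible in essentially one direction only. Even if 7.2 prevails, the post rate on 500 cannot be computed from data, since 50 of the 500 are declared unobserved.

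**Working it through.** **Inputs (Section 7.2, Sub-study, unless noted).** N = 500; current at baseline 50; mailed 450; P10 about 0.052; P01 = 0.018; discordant proportion 0.07; odds ratio 2.922; two-sided alpha 0.05. The 450 also appears in 1.2 and 4.3.1.

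**1. Reproduce the plan's figure.** From the odds ratio and the discordant proportion, P10 = 0.07 × 2.922/3.922 = 0.05215 and P01 = 0.07/3.922 = 0.01785. Exact McNemar power at N = 500, averaged over the number of discordant pairs, is 80.0%. With the rounded 0.052 and 0.018 it is 79.2%. The continuity-corrected test gives 79.9%, and the uncorrected asymptotic test 84.9%. The stated 80% stands.

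**2. See which patients the calculation needs.**
- P10: 0.052 × 500 = 26 conversions, which must come from the 450 (26/450 = 5.8%).
- P01: 0.018 × 500 = 9 lapses, which must come from the 50 current at baseline (9/50 = 18%).

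The 10% baseline is not itself a McNemar input. N = 500 and P01 > 0 are, and both require baseline-current patients in the cohort.

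**3. Apply the Section 3 criteria.** The cohort is 500 − 50 = 450. The baseline is 0/450 by any listed test, so P01 = 0 by selection and the odds ratio P10/P01 is undefined. The N = 500, odds ratio 2.922 statement has no counterpart. With an empty opposite cell, 6 conversions (6/450 = 1.3%) give exact two-sided p = 2 × 0.5^6 = 0.031. At 26/450 the power exceeds 0.9999.

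One qualification applies: 4.3.6 counts Cologuard as screening at EHR review, but 3.1.3/3.2.3 do not list it. A patient current only by that test could enter, so the baseline is essentially, not necessarily exactly, 0%.

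**4. Compare what would be reported, at the plan's 26 conversions.**

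| Cohort | Baseline | Post | Change |
|---|---|---|---|
| Section 3 (450) | 0/450 = 0% | 26/450 = 5.8% | +5.8 points |
| 7.2 (500), no lapses counted | 50/500 = 10.0% | 76/500 = 15.2% | +5.2 points |
| 7.2 (500), 9 assumed lapses | 50/500 = 10.0% | 67/500 = 13.4% | +3.4 points |

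The post rates differ by 15.2 − 5.8 = 9.4 or 13.4 − 5.8 = 7.6 points, most of which is the 10-point baseline offset. The changes differ by 5.8 − 5.2 = 0.6 or 5.8 − 3.4 = 2.4 points. Exact McNemar p is 0.006 for 26 v 9 and below 0.001 for 26 v 0.

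**The case against.** The best defence is that the two sections fit together: 500 − 50 = 450. On this view Section 3 governs who takes part, meaning who is mailed and randomised by envelope, while 7.2 sets the wider denominator for Outcome 1. Section 1.1 speaks of screening rates in the age-group cohort at one clinic, and 2.2 defines the outcome as the proportion current before outreach by EHR query. Such a query would be pointless if current patients had already been filtered out.

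This is probably the intent, and it means that 7.2 read alone gives a 10% baseline. A reader might infer from Section 3 that the baseline as written is simply 0%. The documents do not support that: they conflict, and the Cologuard gap prevents even the Section 3 figure from being guaranteed. But no section says that the screening-history rule limits only the mailed set, and none specifies a second query that would supply the 50.

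The defence can also say that the consequence is small. On the size of the change and on significance at the plan's own figures, that is right. A reader might also contrast the 6 conversions needed for significance in the 450 with the 21 needed against 9 lapses in the 500 (21 v 9, p = 0.043; 20 v 9, p = 0.061). That contrast should not be pressed, because the 9 lapses are assumed and will not be observed. With no lapses counted among the 500, 6 conversions suffice there too.

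**Conclusion.** The inconsistency is real and needs correcting. The 500-pair McNemar calculation cannot come from the cohort that Section 3 defines. In the cohort that 7.2 defines, the P01 cell and the post rate depend on an assumption about about 50 unobserved patients. As the plan stands, neither cohort gives the full before/after comparison from data.

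The size is moderate. The reported levels would differ markedly (0% to 5.8%, against 10.0% to 15.2% or 13.4%), but the estimated change moves by only 0.6 to 2.4 points and the test result does not turn on it. It would be wrong to infer that the power arithmetic is faulty, or that the 7.6 to 9.4 point gap in post rates measures bias in the effect. These figures assume the plan's 26 conversions and its 450/50 split. Only a secondary, uncontrolled comparison is touched; the main trial and the randomised envelope comparison are not affected.

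**What to change.** In 7.2 and 7.3.4, with a cross-reference in Section 3, state two things. First, in the sub-study the screening-history criterion governs only who is mailed and randomised. Second, the Outcome 1 denominator is all active, average-risk RCCHC patients aged 45-49 on the index date, whatever their screening history. Then:

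- Run the index-date query without the screening-history filter.
- Replace the 7.2 statement that baseline-current patients will not be observed with a 60-day EHR re-query of the same list. This reverses a stated choice, so it should be made explicitly.
- Report both rates and the McNemar test on that one denominator. Section 7.3.4 currently names a Mantel-Haenszel chi-squared test for Outcome 1, so it should be aligned with 7.2.
- Use one term for the 500 and another for the 450.

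If only the 450 are kept, drop the pre-post McNemar test and its power statement, and report the conversion proportion with a confidence interval.

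The cost is protocol wording, an EHR query and review for about 50 more patients, and no added mailing or contact. The consent waiver in 8.1 is worded for mailed outreach participants, so check that it covers the 50 who are not mailed.

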4.0 STUDY PLAN

4.1 Main Trial Schema

This trial will enroll up to 4,000 patients aged 50-75 years who are not up-to-date with CRC screening. The primary purpose of this study is to assess the effectiveness of mailed FIT outreach on CRC screening completion in a community health center context in both northeastern and western North Carolina, by comparing the proportion of patients screened across two study arms.

All participants assigned to Arm 2 will be eligible to receive two intervention rounds, scheduled about 54 weeks apart. These two intervention rounds will allow us to longitudinally assess adherence to the United States Preventive Services Task Force recommendations for annual screening with FIT (see 1.2). Arm assignment will remain the same across both intervention rounds. Patients will be

included in the second intervention round if they continue to meet the study's IRB-approved inclusion criteria for age, risk, screening history, CRC or colectomy history, and active patient status (seen within the past 18 months). In accordance with clinical recommendations, patients who receive a positive (abnormal) FIT result in the first round will not be included in the second round of FIT mailings (they will not be mailed a FIT).

We anticipate that the approximate time for the study team to complete each of the two rounds of study mailings will be 3 months, and patients' active participation during each round will last from 4 weeks (for patients with a FIT negative result and needed few, if any, reminders to complete the FIT) up to 6 months (for patients with a positive FIT result who need a follow-up colonoscopy, and needed several reminders to complete the FIT). For each round, we will assume that patients who have not completed screening (FIT, screening colonoscopy, or follow-up colonoscopy) after 6 months following the FIT kit mailing, do not intend to do so. We will randomly select an equal number of control group participants to correspond to each mailing wave for intervention participants, and will track both intervention and control participants for the same time period (from Introductory Letter mailing to 6-months post-mailing).

[figure not shown]
Provider surveys: All FQHC providers who deliver care to patients who received a mailed FIT (Arm 2) will be invited to complete a brief (about 18 items) survey to assess their perceptions of the appropriateness, feasibility, and fit of the program. We also will administer a brief (about 13 items) Contextual Determinants Survey to representatives of each FQHC to assess organizational climate, culture, and communication patterns that may affect the implementation of the project. The Contextual Determinants Survey will be administered to providers with leadership roles FQHC, such as the Chief Medical Officer, project champion, Clinic Nurse Managers, and Lead Referral Coordinators. Contextual Determinants Survey participants all have had direct contact with the UNC project team as we collaboratively developed the program.

Provider interviews: Approximately 2-3 months after administering the provider surveys, we will invite a cross-section of up to 20 providers to participate in a semi-structured interview. We will recruit providers who recommend or provide CRC screening to patients of each FQHC (10 providers from each FQHC region). The interviews will allow us to better understand contextual factors that may affect adoption, maintenance, and scalability of the SCORE CRC screening program.

Patient interviews: We will invite up to 30 intervention arm patients (up to 15 from each FQHC) to participate in a semi-structured interview to better understand factors that affect completion of a follow-up colonoscopy following a positive (abnormal) FIT result. A member of the project team will invite patients to participate in an interview least 2 weeks after their final telephone contact with a patient navigator. We will sample purposively to ensure that we include

important and representative perspectives within each FQHC, based on sex, age, race, ethnicity, English/Spanish fluency, and whether the patient completed a follow-up colonoscopy.

Sub-study Schema for Experimental Comparison of Envelope Type (ages 45-49)

All patients enrolled in the sub-study will be eligible to receive 1 round of annual mailed FIT. We anticipate that the approximate time for the study team to complete 1 round of the study mailings (introductory letter, FIT packet, and up to 2 reminder letters) will be about 6 weeks, and patients' active participation will last from 4 weeks (for patients with a FIT negative result and needed few, if any, reminders to complete the FIT) up to 6 months (for patients with a positive FIT

result who need a follow-up colonoscopy, and needed several reminders to complete the FIT).

4.2 Duration of Study

Main Trial

We anticipate that the entire active data collection phase, from randomizing the cohort to assessing screening outcomes via EHR and completing interviews with a subset of patients (see 4.3.6), will be approximately 36 months.

Sub-study (ages 45-49)

We anticipate that the entire active data collection phase, from randomizing the cohort to assessing screening outcomes via EHR will be approximately 6 months.

4.3 Study Details

4.3.1 Cohort Ascertainment

Our study team will work with RCCHC and BRH to identify the population of patients at each site who meet study inclusion criteria (see section 3.1), using an automated query of the EHR at each site. Per protocols from two similar projects, all patients meeting inclusion criteria will be initially included in the study cohort. Because EHR records are based on best available information and may not reflect screenings performed at another facility, our study materials will include a phone number for patients to contact the study team to self-identify as ineligible. We will select patients for inclusion randomly from the cohort and replace as needed to reach the goal of up to 4,000 Main Trial participants from RCCHC and BRH and an additional 450 sub-study participants from RCCHC. Each FQHC will query their own EHR to identify patients who meet eligibility criteria. Designated staff at each FQHC will securely transfer the queried patient information from their EHR to a folder accessible only to IRB-approved study team members on a secure UNC server (UNC Teams folder designated specifically for each FQHC). The data set will contain, but not necessarily be limited to, patient name, age, sex, race/ethnicity, email address, mailing address, primary care provider, and the date of the most recent visit with one of the FQHC's primary care providers. Only authorized clinic and UNC project team representatives will be able to upload or remove data to UNC Teams. Each FQHC site will have its own folder, which will prevent access to data of patients not seen at their clinic. A member of the UNC project team will then transfer the patient data from UNC Teams to a REDCap database accessible only to UNC project team members.

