4.3.2 Randomization

Main Trial (ages 50-75)

At baseline, patients will be randomized 1:1 to Arm 1 (usual care) and Arm 2 (mailed FIT outreach), stratified by site (RCCHC, BRH) and insurance status (Medicare, Medicaid, commercial/private, self-pay/uninsured). The

randomization list will be generated by the study biostatistician using a SAS program for stratified (by site and insurance status) randomization.

Sub-study (ages 45-49)

At baseline, patients will be randomized 1:1 to Arm 1 (experimental arm) and Arm 2 (active comparator arm). The randomization sequence will be generated by the study biostatistician using a SAS program.

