4.3.6 Data Collection

REDCap database: RCCHC and BRH will securely transfer patient information from the EHR to a secure SharePoint folder at UNC. A UNC research assistant will then upload the data to a REDCap database (developed based on two previous completed or ongoing studies). Data will include, but not necessarily be limited to, patient name, age, sex, race/ethnicity, mailing address, identified primary care provider, and if possible, the number of visits within the past 18 months with that provider. The study team has fully executed data use agreements in place with each FQHC. Designated approved members of the research team members will use the REDCap database to document whether patients were mailed a FIT kit and to track the status of FIT kit completion (yes or no), test result (positive or negative), contact with patients who have positive results (yes or no), and receipt of navigation support for colonoscopy (yes or no), including referrals for no-cost follow-up colonoscopy (yes or no) and transportation services (yes or no). Approved members of the UNC research team will also document in the REDCap database whether patients call to report they are ineligible for FIT screening per their screening and relevant medical history (e.g., already completed CRC screening elsewhere, have a medical history that places them at higher than average risk for CRC).

EHR: Each CHC will specify, train, and credential members of the UNC research team to conduct a manual review of participant EHRs 6 months or more after randomization to determine whether patients completed any CRC screening test (FIT, colonoscopy, flexible sigmoidoscopy, Cologuard) and, if so, the test result. As mentioned in the preceding paragraph, these data will be entered directly into the REDCap database by IRB-approved UNC staff members for analysis.

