4.3.7 Number and Duration of Contact with Patients

4.3.7.1 CRC Screening

Patients in the Main Trial control arm (ages 50-75) will not be contacted. Patients in the Main Trial intervention arm (ages 50-75) and patients the Sub-study (ages 45-49) intervention arm and comparator arm will receive an Introductory Letter (first contact) that notifies the patient to expect a FIT kit in the mail. This mailing will allow the study team to identify patients with incorrect addresses before mailing the FIT kit.

After mailing the FIT kit (second contact), the study team will make up to two reminder attempts to follow up with patients in the intervention arm (Arm 2) who have not returned a completed FIT kit. If the FIT kit is undeliverable and returned to the study team because of an incorrect address, the patient will be removed from future Reminder Letter mailings.

Main Trial Patients (ages 50-75) in Arm 2 will receive up to two reminder letters (third and fourth contact). All sub-study patients (ages 45-49) in the intervention and comparator arms also will receive up to two reminder letters (third and fourth contact).

For patients who complete a FIT kit and have a negative result: The patient will be notified of the test result by letter (see section 4.3.5).

For patients who complete a FIT kit and have a positive (abnormal) result: The patients' primary care provider or the primary care provider's designee will notify the patient of the results. After the patient is notified of their positive result, the patient navigator (employed by UNC and credentialed by RCCHC and BRH) will contact the patient by phone or, if phone contact is not successful, by mail to offer information and support for accessing follow-up colonoscopy. Communication will include information about no-cost colonoscopy (for uninsured patients) and transportation service to and from the colonoscopy appointment (for all patients). The patient navigator will call the patient up to three additional times to support the patient in scheduling an appointment for a follow-up colonoscopy, preparing for the colonoscopy procedure, accessing transportation, and financial services, and understanding colonoscopy results. The approximate duration of each phone call will be 5-15 minutes.

The total number of contacts initiated by the study team will range from **3** (Introductory Letter + FIT kit mailing + results letter/call) to **9** (Introductory

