4.5 Removal of Patients from Protocol

We have not identified any factors *a priori* that would lead the Principal Investigator to remove a patient from the study.

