For Aim 2, we will examine intervention implementation outcomes, including the logistical feasibility, patient acceptability, and provider acceptability of a mailed FIT outreach program. To accomplish this aim, we will track and report feasibility and acceptability metrics. For feasibility, we will measure the proportion of bad addresses using the REDCap database. To assess patient acceptability and perceptions of program appropriateness, we will conduct semi-structured interviews with up to 30 patients who had a positive (abnormal) FIT result, were referred for follow-up colonoscopy, and were offered patient navigations services. Invitations will be made on a rolling basis until a sufficient number of patients complete the interviews. Invitation letters will be sent after no more than 6 months after the FIT kit was mailed. To assess acceptability and feasibility from the providers’ perspectives, we will conduct surveys and semi-structured interviews at two time points. For the interviews, the RCCHC or BRH medical director will send an email to the clinician listserv to invite clinicians at the target clinic to participate in a follow-up interview. If this approach does not yield enough clinician participants, UNC project staff will attend regularly scheduled provider meetings to enhance recruitment. Clinician interviews will be conducted in study months 6-12. We will also track and report the proportions of patients who inform us of ineligibility in response to the Introductory Letter and subsequent mailings.

Aim 2 analytic approach: For quantitative assessments, we will use descriptive statistics (e.g., proportions and associated 95% confidence intervals) to characterize feasibility and acceptability measures. For qualitative assessments (i.e., semi-structured interviews), we will perform a thematic analysis of transcribed interview data.

7.3.3 Aim 3

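### Ineligibility can be self-reported only in Arm 2 and only after randomisation, and the plan does not say that replacement has ended by then or that all randomised patients are analysed

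*Combined protocol and SAP*

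**What the plan says.** Section 4.3.1 takes everyone who passes the EHR query into the cohort at first. It concedes that the EHR may miss screening done elsewhere, and therefore "our study materials will include a phone number for patients to contact the study team to self-identify as ineligible". Its next sentence begins "We will select patients for inclusion randomly from the cohort and replace as needed to reach the goal", the goal being up to 4,000 patients in the Main Trial. It does not say what triggers a replacement, when replacement stops, or whether it can happen within one arm.

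Section 4.3.2 randomises 1:1 at baseline. Under section 4.3.3 only Arm 2 of the Main Trial receives mailings, and section 4.3.7.1 adds: "Patients in the Main Trial control arm (ages 50-75) will not be contacted".

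Three places bear on what happens to callers. Under section 4.3.6 staff record in REDCap "whether patients call to report they are ineligible for FIT screening per their screening and relevant medical history". Section 7.3.2 lists the calls as a descriptive Aim 2 result: "We will also track and report the proportions of patients who inform us of ineligibility in response to the Introductory Letter and subsequent mailings". Section 4.5 says that no factor has been identified in advance "that would lead the Principal Investigator to remove a patient from the study".

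Section 7.3.1 describes the Aim 1 outcome as a proportion of the patients who were sent materials. It then specifies a one-sided Mantel-Haenszel comparison of the two arms. Neither that section nor any other defines an analysis set or states an intention-to-treat rule.

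**The concern.** Some patients who pass the EHR query will already have been screened elsewhere. Randomisation spreads them evenly over the arms. In Arm 2 they can learn of the trial, call, and be identified as ineligible. In Arm 1 they cannot, because nobody writes to them. If a call led to removal or replacement, Arm 2 would lose patients who are not due and would seldom have a new screening event within six months, while similar patients stayed in the Arm 1 denominator. The Arm 2 proportion would rise without any effect of the mailing.

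The mailed-only denominator raises the same issue for bad addresses. Section 4.3.7.1 uses the introductory letter to find these before the kit is sent, so on a literal reading such patients could also drop out of Arm 2 alone. At stake is the validity of the primary randomised comparison.

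**Working it through.** **The plan's own figure.** Section 7.2 gives 25% against 17%, one-sided alpha 0.0125, 80% power and 492 per arm per insurance stratum. With pooled variance and no continuity correction,

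n = [z(0.9875)·√(2·0.21·0.79) + z(0.80)·√(0.25·0.75 + 0.17·0.83)]² / 0.08² = [2.2414·0.5760 + 0.8416·0.5732]² / 0.0064 ≈ 491.5, so 492.

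Then 492 × 2 × 4 = 3,936. Both figures reproduce.

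**Inputs for the illustration.** From section 7.2: p = 17% under usual care, 25% under the intervention, and up to 2,000 per arm (1,000 per arm at each of two sites). Assumed, because the plan gives neither: f, the share of Arm 2 removed (2%, 5%, 10%), and q, the screening rate those patients would have had (0 or 5%).

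**Formula.** Removing a share f with rate q changes the Arm 2 rate from p to (p − f·q)/(1 − f). Arm 1 keeps 17%. The same expression applies if the removed patients are replaced by patients like those who remain.

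**No true effect (17% in both arms).** For f = 5% and q = 0: 0.17/0.95 = 17.89%, a gain of 0.89 points. For f = 5% and q = 5%: (0.17 − 0.0025)/0.95 = 17.63%, a gain of 0.63 points.

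| f | Gain, q = 0 | Gain, q = 5% | Rejection, q = 0, 2,000 per arm | Rejection, q = 0, 492 per arm |
|---|---|---|---|---|
| 2% | 0.35 | 0.24 | 2.6% | 1.8% |
| 5% | 0.89 | 0.63 | 6.7% | 3.1% |
| 10% | 1.89 | 1.33 | 24.7% | 7.1% |

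Gains are in percentage points. Rejection is for a one-sided 0.0125 test by the normal approximation, with the arms kept at full size. For example, at f = 5%, q = 0 and 2,000 per arm the standard error is about 0.0120, so the rejection probability is Φ[(0.00895 − 2.2414·0.0120)/0.0120] ≈ Φ(−1.50) ≈ 6.7%, against a nominal 1.25%. Section 7.3.1 states the 0.0125 level for the four insurance-group tests, where 492 per arm is the planned size. The plan gives no alpha for the overall test, so the 2,000-per-arm column applies that level by assumption.

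**Dependence on q.** At q = 17% the gain is zero. At q = 25% it is negative: (0.17 − 0.05·0.25)/0.95 = 16.58%, or −0.42 points at f = 5%.

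**At the planned rates (25% against 17%, q = 0).** The Arm 2 rate becomes 0.25/(1 − f), so the 8-point difference would read 8.5, 9.3 or 10.8 points for f = 2%, 5%, 10%. Patients with bad addresses may simply have the usual-care rate. With q = 17% and f = 5%, (0.25 − 0.0085)/0.95 = 25.42%, and the difference would read 8.4 points.

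**Limit.** To produce the whole 8 points from no effect with q = 0, f would have to be 1 − 17/25 = 32%.

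**The case against.** The strongest reply is that the plan never says callers leave the analysis. The replacement sentence sits under cohort ascertainment, ahead of the randomisation section, and refers to the full Main Trial and sub-study targets, so topping up the sample before randomisation is a natural reading. What the plan does say about callers is that they are logged and counted for Aim 2, and section 4.5 foresees no removals. Undeliverable kits stop further reminder letters, not participation. Section 4.1 follows both arms over the same period, and the EHR outcome review in section 4.3.6 is not limited to one arm. All of this stands, and it is consistent with keeping every randomised patient.

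It does not close the gap. Section 4.3.1 gives the call as the means of correcting the EHR and names no event before randomisation that would require replacing a patient who passed the query. Section 4.5 does not say who is analysed. Section 7.3.1, the one place that states a denominator, ties it to mailing.

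The reply is also right that the size is uncertain. Both f and q are assumptions, and zero events among callers is the unfavourable end. Replacements would come from the same imperfect EHR cohort, so they would not all be truly due.

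**Conclusion.** The gap is real and concerns the primary comparison. The plan leaves room for an exclusion after randomisation that can operate in Arm 2 only, and its stated denominator points that way. If the exclusion were applied, upward bias is the likely direction, because the ineligibility that the protocol itself expects is screening already done elsewhere. Under the assumptions shown, the bias is a fraction of a point to about two points when there is no true effect. That is too small to create the planned 8 points but enough to raise the false-positive rate of a large overall test. The sub-study mails both arms, so this asymmetry does not arise there.

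A reader might go further in three ways that the documents do not support:

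- That Arm 2 is in fact enriched and the effect biased. This requires callers to be dropped or replaced after randomisation, which no section states.
- That section 4.5 contradicts section 4.3.1. The two conflict only if replacement means removing randomised patients. They agree if replacement is confined to cohort selection.
- That the Aim 3 cost per additional person screened is biased in favour of the intervention. Replacement would also add kit and mailing costs to Arm 2, and the net direction has not been worked out.

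**What to change.** - In section 4.3.1, state that selection and replacement end at randomisation, and make the text consistent with section 4.5.
- In section 7.3.1, replace the mailed-only denominator with all randomised patients, analysed in their assigned arm. Name self-reported ineligibles and undeliverable addresses as included.
- State that a call reporting ineligibility serves only to stop further mailings and to supply the Aim 2 proportion in section 7.3.2.
- If a sensitivity analysis leaves out ineligible patients, base it only on EHR records dated before randomisation, applied identically to both arms.

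This is a change of wording and needs no new data. The Arm 2 proportion may look slightly less favourable. There may also be some dilution. If a share f of both arms is not due and has no events, and the planned rates hold for the rest, the difference becomes 8·(1 − f), that is 7.84, 7.60 or 7.20 points for f = 2%, 5%, 10%. Power of an insurance-group test with 492 per arm then falls from 80% to about 79%, 77% or 74%. A comparison of 2,000 per arm at one-sided 0.0125 keeps more than 99.9%.
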